**Impact of Retro-molar pad carving on complete denture wearers satisfaction and quality of life: a cross-over, double-blind clinical trial.**

### **Statistical analysis:**

The SPSS computer software (IBM SPSS Statistics v21.0; IBM Corp., USA) was utilized for the statistical analysis of the collected data in this study. The significance of the conducted statistical results was considered at two tailed  $\alpha$  of .05. Normal distribution of the data was tested utilizing the Shapiro-Wilk test and the skewness test considering skewness z-score threshold values range from -3.29 to +3.29. All the continuous variables were not normally distributed, except for age and OHIP scores before treatment. Descriptive statistics for normally distributed continuous variables (age and OHIP scores before treatment) included the mean, standard error, standard deviation, median, maximum value, minimum value, and confidence intervals. Meanwhile, descriptive statistics for the non-normally distributed continuous variables included the mean, standard deviation, median, interquartile range, minimum value, and maximum value. Categorical variables in this study (presence of redness, erosion, keratosis, ulceration, and denture fissuratum) were presented as frequencies and percentages.

The Wilcoxon Signed Ranks test was used to test paired differences in satisfaction ratings, dentist's evaluations, and OHIP-EDENT scores after using carved and non-carved lower dentures. The Mann Whitney U test was utilized to identify differences in satisfaction ratings, dentist's evaluations, and OHIP-EDENT scores between genders. Spearman's Rho rank correlations were used to identify the correlations between satisfaction ratings, dentist's evaluations, and OHIP-EDENT scores. Associations between identification of lesions following denture use (presence of redness, erosion, keratosis, ulceration, and denture fissuratum) and having the retromolar pad area of the lower denture carved or not were tested via Fisher's Exact test.

The multiple linear regression analysis was used to identify the contribution of having the retromolar pad area carved or not, satisfaction ratings, and dentist evaluation towards the prediction of OHIP-EDENT scores considering the confounding effects of gender and age.

The calculated sample size was 46 participants. A priori power analysis based on linear multiple regression test (G\*Power, version 3.1.9.7; Heinrich-Heine University) calculated the minimum sample size to be 46 participants. The calculation considered a significance level ( $\alpha$ ) of .05, a statistic power ( $1 - \beta$ ) of 0.8, and an effect size of 0.3. Extra participants were recruited to balance for participant drop outs and secure the required minimum sample size. Fifty participants were recruited for the study, and none of participants was lost during the investigation (drop out ratio was 0%). Therefore, 50 participants were finally recruited and completed the study, and had their data collected and analyzed.

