## Results

The data was collected from a total of 49 participants (23 females and 27 males), and was then processed and analyzed. Participants age ranged from 40 to 78 years old (mean age= 62.8 years old, SD= 8.01, SE= 1.145, median= 63.0, 95% CI= 60.51 – 65.12).

Table 1 demonstrates the descriptive statistics for continuous variables in this study including dentist evaluations of dentures, patients' satisfaction with dentures, and OHIP-EDENT scores among the participants of this study. Paired comparisons of carved and non-carved lower dentures showed that patient satisfaction with retention at function ( $P= .002$ ) and comfort during the use of carved lower dentures ( $P= .026$ ) were significantly higher than non-carved lower dentures (Table 1). Furthermore, the patients demonstrated a tendency to be more satisfied with denture retention at rest as well as during eating when used carved lower dentures in comparison to non-carved ones. This difference was not significant but was close to be significant ( $P= .052$ ,

Table 1). In addition, carved lower dentures were associated with lower OHIP scores (better impacts on oral health) than the non-carved lower dentures; however, the difference was not significant ( $P= .055$ , Table 1). Nevertheless, this tendency was confirmed by the Mann Whitney U test as a significant difference was found in the OHIP scores between carved and non-carved lower dentures ( $MWU= 887.0$ ,  $Z= -2.241$ ,  $P= .025$ ). The carved lower dentures were associated with lower OHIP scores indicating better impacts on oral health than the non-carved dentures.

Table 2 presents the distribution (frequencies and percentages) of redness, erosion, keratosis, ulceration, and denture fissuratum following the use of the tested complete denture designs during this study. Redness was the most observed mucosal change, 18.4% with non-carved dentures and 12.2% with carved dentures. No significant differences in mucosal changes were observed between carved and non-carved lower dentures ( $P> .05$ , Table 2).

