Table 5 presents correlations between age, patient satisfaction, and OHIP scores. The results show that older patients were more comfortable with upper dentures than younger patients (Spearman Rho= 0.309,  $P= .031$ , Table 5). Also, higher pain scores were associated with higher OHIP scores (i.e. worse impacts) after using carved ( $P= .001$ ) and non-carved ( $P< .001$ ) lower dentures (Table 5). In addition, lower OHIP scores (i.e. better impacts) were associated with higher satisfaction with retention at rest, retention at function, denture comfort, general satisfaction with dentures, retention during eating, and retention during speaking after using carved or non-carved lower dentures ( $P< .05$ , Table 5). Besides, correlations between age and dentist rating of dentures showed that older participants were found to have better dentist ratings of retention (Sperman Rho= 0.402,  $P= .004$ ) and higher stability (Spearman Rho= 0.402,  $P= .003$ ) of upper dentures than younger participants.

A multiple linear regression analysis was used to identify the contribution of having the retromolar pad area carved or not, satisfaction ratings, and dentist evaluation of dentures towards the prediction of OHIP scores considering the confounding effects of gender and age (Table 6). Being a female, having lower dentist ratings of denture esthetics, and having more pain due to lower dentures were associated with higher scores of OHIP indicating worse oral health impacts

of the prosthesis ( $P < .05$ , Table 6). Being a female was associated with an increase of OHIP scores by 4 units ( $P = .007$ ). Also, for each decreased unit of dentist ratings of denture esthetics, the OHIP scores were increased by 2 units ( $P = .018$ ). Furthermore, for each increased unit of pain levels due to lower dentures, the OHIP scores were increased by 0.7 units ( $P = .020$ ) (Table 6).

Further multiple linear regression analyses were conducted to identify the contribution of having the retromolar pad area carved or not and dentist evaluation of dentures towards the prediction of patient satisfaction with different denture aspects considering the confounding effects of gender and age (Table 7). The results showed that carved lower dentures were associated with 1.144 times higher satisfaction with lower denture retention during function ( $P = .040$ , Table 7). **[name] please note that Being carved or not was significant predictor for retention of the denture during function.**

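### Thirteen carved versus non-carved tests are each judged at an unadjusted .05; the significance claimed for comfort does not survive adjustment, while retention at function does

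*SAP*

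**What the plan says.** **Criterion.** The Statistical analysis section gives one rule for everything: "The significance of the conducted statistical results was considered at two tailed" alpha of .05. It names no primary outcome, order of testing or adjustment.

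**Planned carved versus non-carved test.** "The Wilcoxon Signed Ranks test was used to test paired differences in satisfaction ratings", and the same sentence covers the dentist's evaluations and OHIP-EDENT. Table 1 prints 13 such tests: 4 dentist ratings, 8 patient ratings and 1 OHIP score. General satisfaction is listed for both dentures, but no Z or P is shown for it.

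**Claims.** The Results section makes two claims of significance from these tests. One is for retention at function, with P=.002. The other is for comfort: "comfort during the use of carved lower dentures ( $P= .026$ ) were significantly higher than non-carved lower dentures". For OHIP the paired result is "however, the difference was not significant ( $P= .055$ , Table 1", but a Mann-Whitney test on the same scores (P=.025) is then said to confirm the tendency. The methods plan Mann-Whitney only for gender differences.

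**Regression.** The methods describe one outcome, with carving among the predictors: "towards the prediction of OHIP-EDENT scores considering the confounding effects of gender and age". The Results add more: "Further multiple linear regression analyses were conducted to identify the contribution of having the retromolar pad area carved or not", now predicting satisfaction. Table 7 holds eight such models. Carving falls below .05 in one of them, retention at function (B=1.144, P=.040), and a bold note draws attention to it.

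**The concern.** When 13 comparisons have equal standing and each is read at .05, the 5% error rate applies to each test and not to the set. A sentence that picks out the items below .05 and calls carving significantly better on them carries a larger risk of error than the stated alpha suggests. Comfort is the exposed result, because its P value is only moderately small. Whether carving can be said to improve comfort depends on how these 13 tests are read together.

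The eight extra regressions and the second OHIP test are a separate, smaller matter. They are further looks at the carving effect that the methods section does not describe, and they are read at the same .05.

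**Working it through.** **1. Reproduce Table 1.** Two-sided P = 2Φ(−|Z|).

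| Comparison | Z | Recomputed P | Table 1 P |
|---|---|---|---|
| Retention at function | −3.054 | .0023 | .002 |
| Comfort | −2.225 | .0261 | .026 |
| Retention during eating | −1.944 | .0519 | .052 |
| Retention at rest | −1.943 | .0520 | .052 |
| OHIP | −1.916 | .0554 | .055 |
| Dentist-rated stability | −1.906 | .0567 | .057 |
| Pain | −1.901 | .0573 | .057 |

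The other six (dentist-rated retention, support and esthetics; insertion; smile; speaking) also match, with P from .175 to .943.

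**2. Error over 13 tests if carving has no effect.**
- Any false difference, independent tests: 1 − .95^13 = .487.
- A false benefit of carving only (.025 in that direction): 1 − .975^13 = .280.
- Correlated tests: simulation of 13 equally correlated normal statistics. The correlations are assumptions, since the SAP gives none between the paired differences.

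| Assumed correlation | Any false difference | False benefit of carving |
|---|---|---|
| 0 | 49% | 28% |
| 0.5 | 33% | 17% |
| 0.7 | 24% | 12% |

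**3. Adjusted P over the 13 tests.**
- Holm: retention at function .00226 × 13 = .029; comfort .0261 × 12 = .313; eating .0519 × 11 = .571. All others are at least .571.
- Hommel: comfort .209.
- Benjamini-Hochberg: comfort takes the smallest value of P × 13/rank at or above its own rank. That occurs at rank 7: .0573 × 13/7 = .106.

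**4. Does the choice of family matter?** Holm-adjusted comfort:
- five lower-denture patient items: .0261 × 4 = .104
- eight patient items: .0261 × 7 = .183
- eight patient items plus OHIP: .0261 × 8 = .209
- Table 1 plus the five lesion tests of Table 2 (18 tests): .0261 × 17 = .443

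Comfort passes Holm only in a family of two with retention at function, or if it is tested alone. Adding general satisfaction makes 14 tests, and retention at function is then at most .00226 × 14 = .032.

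**5. Table 7, taken separately.** The eight carving P values are .394, .040, .353, .796, .388, .265, .930 and .464. Holm on the smallest gives .040 × 8 = .32. In the comfort model carving has B=.412, P=.353.

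**The case against.** **A primary outcome may be named in the protocol.** If comfort were the sole primary outcome, P=.026 would stand without adjustment. Nothing in the SAP points that way, and its title names satisfaction and quality of life. The conclusion must still be conditional on this.

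**The family is chosen by the reviewer, after the results are known.** The 13 tests mix dentist ratings, patient ratings and OHIP, and Holm makes no use of their correlation. This is fair, and .31 should be read as one value in a range. A step-down minimum-P calculation gives comfort about .19 or .14 at assumed correlations of 0.5 or 0.7. All these values are above .05.

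**The reporting is open.** Z and P are printed for all 13 comparisons, the near misses are stated to be non-significant, and the extra regressions are introduced as further analyses. Unadjusted exploratory reporting can be legitimate. But nothing here is labelled exploratory, and comfort is called significantly higher.

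**Stronger readings that a reader might infer, and that the SAP does not support:**
- *The added regressions undermine the comfort result.* They do not bear on it. The text makes no claim about carving and comfort from Table 7. The P=.353 there comes from a model adjusted for pain and dentist ratings, so it neither supports nor refutes the paired result.
- *The benefit in retention at function falls too.* It survives Holm over the 13 Table 1 tests. The Table 7 P=.040 is a second look at that same outcome, and its failure over eight models does not cancel the paired result. Only pooling every carving test in the document (28, including repeat analyses of the same outcomes) takes it to .063.
- *There is a 49% chance of a false benefit of carving.* That figure counts false differences in both directions and assumes independence. The figure for benefit is 28% under independence and lower under positive correlation.
- *Carving does not improve comfort.* Failing adjustment leaves the question open; it is not evidence of no effect.

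**Conclusion.** The point holds for comfort. Under the SAP's rule, the 13 tests in Table 1 carry a 24% to 49% chance of at least one false difference, and about 12% to 28% of at least one false benefit of carving, for correlations between 0.7 and 0. The significance claimed for comfort is not supported after adjustment (.31 Holm, .21 Hommel, .11 Benjamini-Hochberg), and it fails in every family examined of five or more tests. Retention at function keeps its Table 1 claim at .029. This rests on the printed Z values and on the protocol not naming comfort as the sole primary outcome.

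Separately, the Table 7 models and the Mann-Whitney retest of OHIP are not in the methods section and cannot serve as confirmation. The planned paired OHIP result, P=.055, remains non-significant.

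**What to change.** 1. State in the Statistical analysis section whether the protocol names a primary outcome. Unless it names comfort alone, apply Holm across the Table 1 carved versus non-carved comparisons, with the missing general satisfaction test added.
2. Add a column of Holm-adjusted P values to Table 1 and call significant only what survives.
3. In Results, report comfort (P=.026) as an unadjusted exploratory finding.
4. Label the eight Table 7 satisfaction models as post hoc, and make no confirmatory claim from the carving coefficient with P=.040.
5. Label the Mann-Whitney comparison of OHIP (P=.025) as unplanned and remove the statement that it confirms the tendency.

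The cost is one extra column, one further paired test from data already collected, and a few sentences. Comfort loses its significant label; retention at function keeps its own.

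### The cross-over is analysed by a signed-rank test pooled over order of wear, with no period or sequence term; the harm depends on a period effect and sequence counts that the SAP does not give

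*SAP*

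**What the plan says.** The title describes "a cross-over, double-blind clinical trial". For the comparison of the two lower dentures, the Statistical analysis section states: "The Wilcoxon Signed Ranks test was used to test paired differences in satisfaction ratings". The same test is applied to the dentists' ratings and to OHIP-EDENT, again carved against non-carved. Significance is two-sided at .05.

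Nothing in that section, in the Results text or in Tables 1 to 7 mentions period, sequence or order of wear. The predictors in Table 6 are gender, age, carved or not, dentist ratings and patient ratings (pain and satisfaction). Those in Table 7 are gender, age, carved or not, dentist ratings and pain. Neither has a period, sequence or patient term. The additional Mann-Whitney test on OHIP in the Results also has no period term. No result or count is given by sequence.

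On numbers, the Results say: "The data was collected from a total of 49 participants (23 females and 27 males"). The two sex counts add to 50, while the frequencies in Table 2 add to 49.

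**The concern.** In a two-period cross-over, each patient's carved minus non-carved difference contains the treatment effect plus or minus any change between the first and second period. The sign depends on which denture was worn first. A signed-rank test on the pooled differences treats that systematic part as random scatter. With equal sequences it averages out of the estimate but stays in the spread. With unequal sequences part of it stays in the estimate.

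Two things are at stake. One is power for outcomes near the threshold: in Table 1, retention at rest and retention during eating have P = .052, OHIP has P = .055, and pain and dentist-rated stability have P = .057. The other, if the sequences are clearly unequal, is bias and a type I error above 5%. Patients may adapt to new dentures over time, so a period effect is plausible, but the document does not show one.

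**Working it through.** **Inputs from the SAP.** OHIP after non-carved: mean 11.12, SD 7.793. OHIP after carved: mean 8.45, SD 6.433. Difference 11.12 − 8.45 = 2.67, with Z = −1.916 and P = .055 (Table 1). N is taken as 49, from the Results and the Table 2 frequencies.

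**Inputs not in the SAP (assumed).** The period effect π, the sequence sizes n1 and n2, and the SD of the paired differences within a sequence. The SAP has no figure of its own for a period effect. Its sample size of 46 was computed for a multiple regression and does not bear on this point.

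**Choice of SD.** Dividing Z by √N gives a standardised difference of 1.916/7 = 0.274, which implies a pooled SD of about 2.67/0.274 = 9.7 (approximate). That pooled SD would already contain any period effect. The main assumption is a within-sequence SD of 8.5, with 9.7 as the alternative.

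**Model.** The paired difference is τ + π in one sequence and τ − π in the other, plus error with standard deviation σ. Then:
- bias in the pooled mean = π(n1 − n2)/N
- inflation of the SD = √[1 + (π/σ)²(1 − ((n1 − n2)/N)²)]

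**Bias as a share of π.**
- 25/24: 1/49 = 0.02
- 27/22: 5/49 = 0.10
- 30/19: 11/49 = 0.22
- 33/16: 17/49 = 0.35

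For a 5-point effect this is 0.10 OHIP points at 25/24 and 5 × 11/49 = 1.12 points at 30/19, against the observed 2.67.

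**Power at 25/24.** Simulation with normal errors, true effect 2.67 and SD 8.5. The plain signed-rank test is compared with a rank-sum test of within-patient period differences between sequences:
- no period effect: 55% against 55%
- 2 points: 55% against 55%
- 3 points: 53% against 56%
- 5 points: 45% against 54%

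With SD 9.7 the 5-point case gives 38% against 45%, and no period effect gives 47% against 47%.

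**Type I error, plain against adjusted, with π in SD units of the paired difference.**
- 25/24: 3.0% against 5.0% at 0.5 SD; 0.5% against 4.9% at 1 SD
- 27/22: 3.6% against 4.9% at 0.5 SD; 1.7% against 5.1% at 1 SD
- 30/19: 8.2% against 4.8% at 0.5 SD; 11.6% against 4.9% at 1 SD
- 33/16: 16.4% against 5.3% at 0.5 SD; 39.0% against 4.6% at 1 SD

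In OHIP points, 30/19 with a 5-point effect gave 8.9% to 9.7% in repeated runs at SD 8.5 (adjusted 4.3% to 4.5%), and 8.2% at SD 9.7 (adjusted 4.5%).

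**The case against.** The strongest reply is that the harm needs inputs nobody has shown. For effects of 2 to 3 points at 25/24 the loss is nil to 3 percentage points. At 27/22 the type I error is not inflated. Inflation needs a marked imbalance together with a sizeable period effect, and nothing in the document points to a 30/19 split. Under unrestricted randomisation, which is itself an assumption, a split at least that uneven would occur about 15% of the time. All of this stands, and it limits the point to a conditional one.

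A reader might infer more in four ways, none of which the document supports:
- **That the fall in OHIP from 22.59 before treatment to 11.12 and 8.45 shows a large period effect.** It compares scores before and after new dentures, which both conditions share. It says nothing about change from the first period to the second.
- **That the power loss could be very large, for example with an 8-point effect.** With SD 8.5 the pooled SD would be √(8.5² + 8²) = 11.7. The printed SDs give √(7.793² + 6.433²) = 10.1 at zero correlation, so 11.7 would need a within-patient correlation of about −0.34. That fits Table 1 poorly. The 5-point case gives √(8.5² + 5²) = 9.9, which is compatible with Table 1 but not shown by it.
- **That the unpaired OHIP test giving P = .025 against the paired .055 reveals a period effect.** Low within-patient correlation would explain it equally well.
- **That 49 patients make bias certain.** An odd number does rule out an exactly equal split, but 25/24 leaves only 2% of the period effect, and the document is not consistent on whether 49 or 50 were analysed.

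One objection does not stand: that this belongs to the protocol. The choice of test and of the terms in it is fixed in the SAP's own analysis section.

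**Conclusion.** The omission is real. A trial described as a cross-over has no analysis that accounts for period or sequence, although a period-adjusted test costs almost no power when there is no period effect. Its consequence cannot be calculated from the document. Under the assumptions shown, the loss is negligible for small period effects with near-equal sequences and about 9 percentage points of power for a 5-point effect. A split such as 30/19 with a 5-point effect would give about 1.1 OHIP points of bias and a type I error of about 9%.

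The omission does not by itself undermine the results for retention at function (P = .002) or comfort (P = .026): with near-equal sequences the plain test is conservative. Nor does it show that the results at P = .052 to .057 would change; that is unknown until the data are analysed by sequence. The change should be made, and it would matter more if the sequence counts prove clearly unequal.

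**What to change.** 1. Report the number of patients in each sequence, with the outcome means by sequence and period.
2. For OHIP and every rating, add a period-adjusted analysis. Either compare within-patient period differences between the two sequences by the rank-sum test, with a Hodges-Lehmann estimate of the carving effect and its 95% CI, or fit a mixed model with treatment, period, sequence and a random patient effect.
3. Present it for all outcomes beside the signed-rank results and label it post hoc. The results are already known, so replacing the test now, or adjusting only the near-threshold outcomes, would be a data-driven choice.

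The cost is added SAP text and a re-run, with no new data, provided that order of wear was recorded. A cross-over requires this, though the document does not state it. If there is no period effect and the sequences are near equal, the loss of power is negligible (55% against 55% in the simulation above).
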